- The appetite-stimulating hormone ghrelin is produced by ghrelinergic cells in the gut and acts as a peripheral orexigenic signal that communicates with the arcuate nucleus of the hypothalamus to increase appetite and food intake in response to fasting (Khan et al 2018). In healthy individuals, fasting promotes increased secretion of ghrelin in the gut, and levels decrease after eating; however, this does not occur in patients with PWS. Children and adults with PWS have between 3.0- and 4.5-fold higher fasting plasma levels of ghrelin compared with matched control patients with obesity (Cummings et al 2002; DelParigi et al 2002; Haqq et al 2003), and ghrelin levels may influence eating behavior in these patients (Allas et al 2018). The mechanism underlying ghrelin dysregulation and the functional impact of elevated ghrelin levels on symptoms of PWS, including hyperphagia, are currently unknown; however, a link between ghrelin and the histaminergic system has been suggested by studies investigating the gastroprotective role of ghrelin in the gut (Adami et al 2010). In this study, serum ghrelin levels (acylated and unacylated) will be evaluated (Section 6.3.10).

Standard safety and tolerability assessments will include adverse event (AE) monitoring, clinical laboratory tests, vital signs, 12-lead electrocardiograms (ECGs), physical examinations, and suicidality. In addition, anxiety will be assessed using the Anxiety, Depression, and Mood Scale (ADAMS), and the frequency, type, and duration of seizures in patients with a history of seizure disorder will be collected (Section 6.5.6).

Characterization of the pharmacokinetics (PK) of pitolisant will inform the optimal dose selection strategy. Pitolisant is primarily metabolized by cytochrome P450 (CYP) 2D6 and to a lesser extent by CYP3A4; metabolites are further metabolized or conjugated with glycine or glucuronic acid. None of the pitolisant metabolites are pharmacologically active. BP1.3484 is the most predominant metabolite after repeat dosing with pitolisant, and PK analyses in this study will include evaluation of this major metabolite.

1.3. Dose Rationale

1.3.1. **Age-Based Dosing**

Eligible patients (60 in total) will be randomized at a 1:1:1 ratio to one of three treatment groups: higher dose pitolisant, lower dose pitolisant, or placebo (20 patients per group).

The doses for each age range (Table 8) were selected based on safety and efficacy data from the clinical development program for adults with narcolepsy and PK data from 24 pediatric patients with narcolepsy (ages 7 to <18 years) receiving a single dose of pitolisant. The pitolisant dose for adult patients is consistent with the FDA-approved United States Prescribing Information (USPI). The pediatric age-based doses were chosen based on modeling using the PK data available from the 24 pediatric patients with narcolepsy, which suggest that pediatric patients have higher exposure to pitolisant than adults. The titration period is consistent with the FDA-approved United States Prescribing Information (USPI).

1.3.2. Dosing (OLE Phase After Implementation of Protocol Amendment 6)

The dosing regimens (Table 9) were selected based on:

- Efficacy signals that were observed for the higher dose pitolisant treatment group in the completed Double-Blind Treatment Phase of this study, suggesting a target for dosing of approximately mg/kg.
- Population PK simulations:
 - Area under the curve during a dosing interval at steady state (AUCtau) and maximum observed concentration (Cmax) in patients with PWS receiving the dosing regimens were similar to those in patients with narcolepsy receiving the doses included in the FDA-approved prescribing information for WAKIX (pitolisant).
 - The estimated risk of QT interval prolongation in patients with PWS using the dosing regimens described in Table 9 is consistent with the risk described in patients with narcolepsy in the FDA-approved prescribing information for WAKIX (pitolisant).
- Safety data:
 - Pitolisant is well tolerated in adult and pediatric patients with narcolepsy and in ongoing clinical development programs at doses up to 35.6 mg once daily.
 - Pitolisant is well tolerated in adult and pediatric patients with PWS at doses up to 35.6 mg in the Double-Blind Treatment Phase of this study and up to mg in studies HBS-101-CL-003 and HBS-101-CL-004.

- The safety/tolerability profile of pitolisant in pediatric patients is generally consistent with the established safety/tolerability profile in adult patients.
- No dose-related adverse effects were identified in the pooled narcolepsy New Drug Application (NDA) safety population of 1513 patients who received pitolisant 17.8 mg or 35.6 mg once daily for a mean of 33 weeks.

During the OLE Phase, pitolisant dose can be adjusted (higher or lower) based on Investigator discretion (Section 3.1.5.2).

1.4. Potential Risks and Benefits

The overall safety/tolerability profile of pitolisant at doses of 4.45 to 35.6 mg once daily has been well characterized from 41 completed studies. Of the 41 completed studies, 19 were Phase 1 studies and 22 were Phase 2/3 studies in the indications of narcolepsy, obstructive sleep apnea, Parkinson's disease, epilepsy, schizophrenia, Lewy body dementia, and attention deficit hyperactivity disorder (i.e., 8 narcolepsy and 14 non narcolepsy studies). The Phase 2/3 data comprised a total of 1513 patients who were treated with pitolisant; 1043 of these patients received pitolisant in double-blind, placebo-controlled studies. The most frequently reported (≥5%) treatment-emergent AEs (TEAEs) in patients who received pitolisant in the Phase 2/3 studies were headache (13.5%), insomnia (8.5%), and nausea (5.8%); the majority of these events were considered treatment-related.

Pitolisant is extensively metabolized by the liver and there is a significant increase in pitolisant exposure in patients with moderate hepatic impairment. Pitolisant prolongs the QT interval. The use of pitolisant should be avoided in patients with known QT prolongation or in combination with other drugs known to prolong the QT interval. Pitolisant should also be avoided in patients with a history of cardiac arrhythmias, as well as other circumstances that may increase the risk of the occurrence of torsade de pointes or sudden death, including symptomatic bradycardia, hypokalemia or hypomagnesemia, and the presence of congenital prolongation of the QT interval. The risk of QT prolongation may be greater in patients with hepatic or renal impairment due to higher concentrations of pitolisant. Pitolisant is contraindicated in patients with severe hepatic impairment and is not recommended in patients with end-stage renal disease.

In the clinical development program for pitolisant, there was no evidence of withdrawal syndrome from pitolisant or rebound effect upon discontinuation of therapy, and long-term studies did not demonstrate evidence of the development of tolerance to pitolisant. There were no clinically relevant effects of pitolisant on vital signs, electrocardiographic parameters, or laboratory findings across the database of patients exposed to pitolisant.

Additional information is provided in the WAKIX (pitolisant) Investigator's Brochure (IB) and current prescribing information for WAKIX (pitolisant).

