4.1.2. Exclusion Criteria

A patient who meets any of the following criteria will be excluded from enrollment in the study:

- 1. Has a diagnosis of another genetic or chromosomal disorder distinct from PWS.
- 2. Has untreated OSA or is at high risk for OSA based on medical history and clinical assessment; or, has another relevant underlying sleep disorder that in the opinion of the Investigator is the primary contributing factor to the patient's EDS.
- 3. Consistently consumes >600 mg of caffeine per day and is unable/unwilling to reduce caffeine intake to <600 mg per day for the duration of the Double-Blind Treatment Phase of the study; caffeine intake should remain consistent during Screening and throughout the Double-Blind Treatment Phase of the study.
- 4. Does not agree to discontinue any prohibited medication or substance listed in the protocol (Section 5.7.2).
- 5. Participation in an interventional research study involving another investigational medication or device in the 28 days prior to enrollment and for the duration of the Double-Blind Treatment Phase of the study, unless the Investigator consults with the Medical Monitor and obtains written approval for the patient to enroll; patients who complete a washout of an investigational medication of at least 5 half-lives or 14 days (whichever is longer) may be enrolled in the Double-Blind Treatment Phase of the study. Patients considering participation in another interventional research study in the OLE Phase must consult with the Investigator who will consult with the Medical Monitor.
- 6. Has a primary psychiatric diagnosis with current active symptoms of psychosis or schizophrenia.
- 7. Has a diagnosis of end-stage renal disease (eGFR of <15 mL/minute/1.73 m²) or severe hepatic impairment (Child-Pugh C).

- 8. Has a diagnosis of moderate or severe renal impairment (eGFR ≥15 to ≤59 mL/minute/1.73 m²) or moderate hepatic impairment (Child-Pugh B) at Screening or during the Double-Blind Treatment Phase.
- 9. Has abnormal laboratory values at Screening that are clinically significant as determined by the Investigator.

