4.4. Patient Withdrawal and Follow-up

4.4.1. Patient Withdrawal

Patients are free to withdraw from the study at any time for any reason. A patient may also be withdrawn from the study by the Investigator or the Sponsor at any time for safety, behavioral, or administrative reasons if either determines that it is not in the patient's best interest to continue participation.

Possible reasons for early withdrawal include:

- AE
- Lack of effect
- Patient/parent(s)/legal guardian(s) decision
- Lost to follow-up
- No longer meets eligibility criteria
- Non-compliance with study protocol
- Non-compliance with study drug treatment
- Other, with specific reason (e.g., pregnancy)

Patients who develop end-stage renal disease (eGFR of <15 mL/minute/1.73 m²), severe hepatic impairment (Child-Pugh C), or any other medical condition that in the opinion of the Investigator may pose a risk to the patient must be discontinued from the study.

The following ECG findings, based on the mean of triplicate 12-lead ECGs, require discontinuation from the study:

- Mean QTcF >500 ms
- Mean QTcF increase from Screening >60 ms AND mean QTcF >470 ms
- Heart rate increase from Baseline >65% or decrease from Baseline >40%

Any patient with a new positive response on question 4 (active suicidal ideation with some intent to act, without specific plan) and/or question 5 (active suicidal ideation with specific plan and intent) of the Very Young Child/Cognitively Impaired-Since Last Contact C-SSRS (Appendix M) will be discontinued and will require further evaluation by the Investigator.

The date and primary reason for early withdrawal will be recorded in the electronic case report form (eCRF). At the time of withdrawal from the study, every attempt should be made to complete the Early Termination (ET) Visit assessments (Section 7.3.3 and Section 7.4.3).

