6.5.3. Vital Signs

Vital signs will include blood pressure, heart rate, respiratory rate, and body temperature and will be measured at on-site study visits as detailed in Section 7. Patients should be resting for at least 5 minutes before measuring vital signs.

Vital sign measurements will be performed before blood samples are collected for clinical laboratory testing.

6.5.4. 12-Lead Electrocardiograms

12-lead ECGs will be obtained in triplicate for all patients at every on-site study visit as detailed in Section 7. Patients should be resting for at least 5 minutes before the first ECG is performed. All pediatric 12-lead ECGs will be read by a pediatric cardiologist.

ECG testing is to be performed before blood samples are collected for clinical laboratory testing.

Electrocardiogram findings that require discontinuation from the study are specified in Section 4.4.1.

In the Double-Blind Treatment Phase, clinically significant ECG findings (other than those requiring discontinuation from treatment) will require evaluation by the Investigator in consultation with the Medical Monitor.

In the OLE Phase and as noted in Section 4.4.2, any ECG reading that demonstrates QT prolongation should be promptly addressed by the Investigator. For clinically significant ECG findings, a follow-up ECG should be performed within 24 hours and again 7 days later to ensure the abnormality is not worsening. Follow-up 12-lead ECGs may be performed locally, with the results sent to the Investigator. At the discretion of the Investigator and in consultation with the Medical Monitor, pitolisant dosing may be temporarily stopped (interrupted) for 2 to 3 days based on clinically significant ECG findings. During an interruption, 12-lead ECGs will be performed daily. Upon resolution of the ECG abnormality, pitolisant administration may resume at the same dose as before the interruption, or the pitolisant dose may be lowered by 50%. If the condition persists after the interruption in dosing, the Investigator, in consultation with the Medical Monitor, will decide whether treatment should be permanently discontinued.

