6.5.5. Clinical Laboratory Tests

Clinical laboratory tests will include serum chemistry, hematology, urinalysis, pregnancy tests (serum and/or urine), and urine drug screens as detailed in Table 11. Samples for clinical laboratory tests (serum chemistry and hematology) will be collected as outlined in Section 7.

Consistent with the NIH Pediatric Blood Volume for Research Guidelines (Howie 2011), the total volume of blood collected is not to exceed the maximal allowable amount of 3.0 mL/kg per day (Appendix A). The approximate amount of blood to be collected for clinical laboratory tests at each visit is 9.0 mL (5.0 mL for serum chemistry tests and 4.0 mL for hematology tests).

The Laboratory Manual provides detailed instructions on sample collection, processing, and shipping procedures.

Laboratory test results will be reviewed by the Investigator. Any laboratory value outside of the normal reference range will be evaluated for clinical significance and, if deemed clinically significant, should be reported as an AE with an appropriate diagnosis.

Table 11: Clinical Laboratory Tests

| Urine Drug Screen -Amphetamines/stimulantsa -Barbiturates -Benzodiazepines -Cocaine metabolites -Opiates -Tetrahydrocannabinol -Phencyclidine Urinalysis -Specific gravity -pH -Blood -Glucose -Protein -Leukocyte esterase -Ketones -Bilirubin -Nitrites -Casts -Crystals -Erythrocytes -Renal tubular epithelial cells -WBCs -Bacteria Serum Drug Screen -Cannabidiola | Serum Chemistry (5.0 mL blood sample) -Albumin -Alkaline phosphatase -Alanine aminotransferase -Aspartate aminotransferase -Blood urea nitrogen -Calcium -Chloride -Creatinine -Creatine kinase -Glucose -High-density lipoprotein -Low-density lipoprotein -Phosphorus -Potassium -Sodium -Total bilirubin -Direct bilirubin -Total cholesterol -Total protein -Triglycerides -Uric acid -Ghrelin ^{a,b} Hematology (4.0 mL blood sample) -Complete blood count, including platelet count and WBC count with differential -Hemoglobin |
|---|--|
| Serum Drug Screen | |

FCBP = female of child-bearing potential; HbA1c = hemoglobin A1c; WBC = white blood cell

Note: Parameters will be assessed at study visits as detailed in the Schedule of Assessments for the Double-Blind Treatment Phase and the Schedule of Assessments for the OLE Phase.

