Patients remaining in the study and receiving study drug after TC 8 will return with their caregivers to the study site on Day 549 ± 7 days (Visit 10) and approximately every 6 months (180 days ± 7 days) thereafter until either the patient withdraws from the study or the Sponsor elects to terminate the study; these patients may complete one on-site study visit remotely per year (Section 6.6 describes assessments associated with on-site study visits that may be completed remotely).

Patients will be dispensed study drug for 3 months (i.e., 90 days) for once daily administration, which is a quantity sufficient until the next scheduled telephone call.

The following assessments will be performed at Visit 10 and at each subsequent study visit:

- Urine pregnancy test (FCBP only)
- Full physical examination
- Body weight and height
- Vital signs
- 12-lead ECG (in triplicate)
- C-SSRS (Appendix M)
- ADAMS
- Clinical laboratory tests (serum chemistry, hematology, urinalysis)
- Urine drug screen
- Review of AEs
- Review of concomitant medications
- ESS-CHAD (parent/caregiver version)
- CaGI-S (for EDS)
- CGI-S (for overall clinical status related to PWS)
- Review study drug compliance/accountability (Section 5.5 and Section 5.6)

Patients will be dispensed study drug in a quantity sufficient for 3 months (i.e., 90 days) of once daily administration at each visit.

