Appendix 6 Clinical Laboratory Tests

-Amphetamines/stimulants^a

-Barbiturates -Benzodiazepines -Cocaine metabolites

-Opiates

-Tetrahydrocannabinol

-Phencyclidine

Urinalysis

-Specific gravity

-pH -Blood -Glucose -Protein

-Leukocyte esterase

-Ketones -Bilirubin -Nitrites -Casts -Crystals -Erythrocytes

-Renal tubular epithelial cells

-WBCs -Bacteria

Serum Drug Screen

-Cannabidiol

Pregnancy Screen (FCBP only)

-Serum (at Screening only) -Urine (as scheduled after

screening)

-Albumin

-Alkaline phosphatase -Alanine aminotransferase -Aspartate aminotransferase

-Blood urea nitrogen

-Calcium

-Chloride -Creatinine

-Creatine kinase

-Glucose

-High-density lipoprotein -Low-density lipoprotein

-Phosphorus -Potassium -Sodium

-Total bilirubin -Direct bilirubin -Total cholesterol -Total protein -Triglycerides

-Uric acid -Ghrelin^b

Hematology (4.0 mL blood sample)

-Complete blood count, including platelet count and WBC count

with differential -Hemoglobin -Hematocrit

-HbA1c

Abbreviations: FCBP = female of child-bearing potential; HbA1c = hemoglobin A1c; WBC = white blood cell

Note: Parameters will be assessed at study visits as detailed in the Schedule of Assessments for the Double-Blind Treatment Phase and the Schedule of Assessments for the OLE Phase.

^a Stimulants are tested in the Double-Blind Treatment Phase only.

b Acylated and unacylated ghrelin; patient must be fasting. Blood sample for ghrelin measurement may be taken at the same time as clinical laboratory test sample.

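### Section 1.4 advises against pitolisant in hypomagnesemia, but no scheduled test measures magnesium, and the gap remains open in the OLE

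*Protocol*

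**What the plan says.** Protocol Section 1.4 states that pitolisant prolongs the QT interval. It advises against use in circumstances that may raise the risk of torsade de pointes or sudden death, "including symptomatic bradycardia, hypokalemia or hypomagnesemia, and the presence of congenital prolongation of the QT interval". Low potassium and low magnesium are named together.

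The scheduled panel is in Protocol Table 11 (Section 6.5.5). Its serum chemistry column includes "Low-density lipoprotein -Phosphorus -Potassium -Sodium" but has no entry for magnesium. SAP Appendix 6 gives the same list ("Phosphorus -Potassium -Sodium"). The laboratory footnotes to both protocol schedules of assessments, double-blind and OLE, point to Table 11.

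Two provisions act on laboratory results. Exclusion 9 removes a patient who "Has abnormal laboratory values at Screening that are clinically significant as determined by the Investigator". Section 6.5.5 says "Any laboratory value outside of the normal reference range will be evaluated for clinical significance". Neither names an analyte.

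QT safety is otherwise handled by ECG. Section 4.4.1 requires discontinuation on several ECG criteria, among them "Mean QTcF increase from Screening >60 ms AND mean QTcF >470 ms". For a clinically significant ECG finding in the OLE, Sections 4.4.2 and 6.5.4 provide for repeat ECGs and, at discretion, a 2 to 3 day interruption. Then: "Upon resolution of the ECG abnormality, pitolisant administration may resume at the same dose as before the interruption", or the dose may be halved. No electrolyte test is named.

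**The concern.** The protocol tells investigators to avoid the drug in a condition that its own scheduled tests cannot reveal. Exclusion 9 and the Section 6.5.5 review work on the results that come back from the laboratory. A magnesium value never comes back, so neither can act on it.

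The stake is patient safety in the continuing OLE. When a QT finding arises, the investigator must decide whether to resume the same dose, lower it or stop. The scheduled panels supply a potassium result for that decision and no magnesium result. A correctable contributor could be missed, and it is harder to say whether an individual QT outlier reflects the drug or an electrolyte disturbance. No efficacy endpoint is affected.

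**Working it through.** The plan gives no figure to reproduce. The check compares the risk statement with the tests and rules that would put it into practice, then counts the scheduled opportunities.

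**1. Is magnesium really absent?** The Table 11 serum chemistry column runs from albumin to ghrelin, 22 entries; potassium, calcium and phosphorus are present and magnesium is not. Other parts of Table 11 are damaged in the available text, but this column is intact. SAP Appendix 6 gives the same 22 chemistry entries, and magnesium does not appear there under hematology, urinalysis, drug screens or pregnancy tests either. The absence is not a text-extraction artefact.

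**2. How is each Section 1.4 circumstance covered elsewhere in the protocol?**

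| Circumstance in Section 1.4 | Criterion or scheduled test |
|---|---|
| Known or congenital QT prolongation; arrhythmia | Exclusion 10; ECG rules in 4.4.1 |
| Other QT-prolonging drugs | Exclusion 16; Section 5.7.2 |
| Symptomatic bradycardia | Heart rate in vital signs and ECG; heart-rate rule in 4.4.1 |
| Hepatic or renal impairment | Exclusions 7 and 8; Sections 3.1.5.2 and 4.4.1 |
| Low potassium | Potassium in Table 11 |
| Low magnesium | No specific criterion and no scheduled test |

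Hypomagnesemia is the only one without a specific control, and neither document gives a reason.

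**3. Where can the gap still be closed?** Section 1.3.2 describes the double-blind phase as completed. Section 4.6.1 keeps the OLE open until the Sponsor ends it. The OLE also relaxes some controls on exposure. Strong CYP2D6 inhibitors become allowed, with a stated 2.2-fold exposure increase and a halved dose (Section 5.7.3). Patients who develop moderate hepatic impairment, or moderate or severe renal impairment, may continue with a possible dose decrease (Section 3.1.5.2).

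**4. Scheduled chemistry panels per OLE patient.**

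- Visits 6 to 9: Days 99, 189, 279, 369 = 4.
- From Visit 10, every 180 days: 549, 549 + 180 = 729, 729 + 180 = 909, 909 + 180 = 1089 = 4.
- By Day 1089: 4 + 4 = 8. Adding one at end of treatment or early termination: 8 + 1 = 9.
- Panels with magnesium: 0.

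Day 1089 is only an illustrative horizon, because the OLE has no fixed end.

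**5. Double-blind phase, for the record.** Panels fall at Screening, Baseline and Visits 3, 4 and 5, so 5 per patient and 60 × 5 = 300. If every patient's Screening laboratory tests had been combined with Baseline, as Section 6.6.1.1 allows, the count would be 60 × 4 = 240. This can no longer be changed.

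**6. Would a panel result be there when needed?** In the OLE schedule, ECGs and clinical laboratory tests fall at the same visits. A QT finding on a scheduled ECG would therefore come with a chemistry panel from that visit. After Visit 9 both are scheduled only every 180 days.

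**The case against.** The best case against is that Section 1.4 is a risk summary and not a testing schedule. It creates no duty to test for each circumstance it lists, and no eligibility, withdrawal or dosing rule mentions magnesium, so no protocol commitment is broken.

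The other safeguards are substantial. They include triplicate ECGs with entry and stopping limits, the ban on QT-prolonging drugs, the family-history exclusion, cardiologist reading of pediatric ECGs, and arrhythmia and syncope questions at the safety follow-up calls. Section 1.4 itself reports no clinically relevant ECG or laboratory effects among exposed patients, and Section 1.3.2 says the simulated QT risk under OLE dosing is consistent with the approved labelling. Known hypomagnesemia can surface through medical history or be handled under exclusion 20. Section 7.6 lets an investigator order laboratory tests at an unscheduled visit, and nothing confines the ECG work-up to ECGs.

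Most of this stands, and it limits the seriousness of the point. None of it supplies a specified test. Medical history finds only what is already diagnosed, ECGs show the effect and not the cause, and a discretionary test depends on someone thinking of it.

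Two further criticisms are fair. Counting panels without magnesium describes the omission and does not estimate harm. And adding an analyte to routine panels does not change the work-up in Sections 4.4.2 and 6.5.4, so a finding on an unscheduled ECG could still rest on an older magnesium value.

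**Conclusion.** The concern holds. Section 1.4 names a condition in which the drug should be avoided, and no test specified in the protocol or SAP can identify it. In size this is 0 of 22 chemistry entries, and 0 of 8 scheduled OLE panels per patient by Day 1089 (0 of 9 with the final visit).

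The conclusion is limited to what the protocol and SAP specify. The Laboratory Manual was not available, and discretionary testing remains possible. The documents give neither a prevalence of hypomagnesemia nor an OLE head count, so the number of patients affected is unknown. The randomised QTcF comparison between arms is not biased by the gap. The weight of the point comes from an inexpensive remedy for a safety gap in a phase where dosing continues.

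**What to change.** Add serum magnesium to the serum chemistry list in Protocol Table 11 and SAP Appendix 6. Run it on the existing chemistry sample at every remaining scheduled laboratory visit: Visits 6 to 9, Visit 10 and every 180 days after it, and end of treatment or early termination. The investigator reviews it with potassium under Section 6.5.5. No new threshold or discontinuation rule is proposed.

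The cost is one routine analyte on blood already drawn, with a small laboratory fee and no extra visit. The laboratory must confirm that the 5.0 mL chemistry sample is enough. The change needs a protocol amendment (Section 12.2.1) and IRB approval before it takes effect (Section 11.3). SAP Section 6.0 already expects updates when the protocol changes, and SAP Section 9.6 plans a separate report for the OLE. Extra screen failures would arise only where screening still applies, and for the completed double-blind phase it does not.
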